11.0. Missing Data

The clinical investigation team will make substantial efforts to ensure complete collection of data for all patients, and to ensure minimal loss to follow-up to optimize evaluation of the primary effectiveness outcome. For the primary analyses, we will analyze those patients who have follow-up data. Any missing data will be assumed to be missing at random (MAR) given the adjustment of baseline covariates. However, in the event that a patient is lost to follow-up, the underlying reason(s) for dropping out will be tracked in order to help assess the mechanisms of missingness. We will analyze missing data and conduct sensitivity analyses as required (i.e., >15% missing outcome follow-up at 3 months or differential missingness by group). Specifically, we will address missing data in two ways. Our first approach will apply a pattern mixture imputation missing data approach that relaxes the MAR assumption conditioning on the patterns of missing data over time among those with at least one follow-up time measure and inverse probability weights (IPW) for those missing all follow-up time points.¹⁹ The second approach will be used as a sensitivity analysis assuming a worst-case, best-case approach. Specifically, for those with missing outcome data in the intervention arms we will assume they did not achieve the MCID in pain severity at each missing time point (worst-case). For those randomized to the usual care we will assume all achieved the MCID in pain severity at each missing time point (best-case). This sensitivity analysis will provide the extreme case in how small the intervention effect could be relative to usual care due to missing outcome data.

12.0. Outlier Measures

The potential for outliers is minimal in our data since most measures are from questionnaires and continuous values are scales (e.g., 11-point Likert score). Therefore, we will not correct for outliers in the analyses involving survey data. In the economic analyses we will assess for the influence of outliers with a sensitivity analysis where we Winsorize outliers to the value of the 99th percentile.

13.0. Demographic and Baseline Characteristics

Demographics will include age, sex, race, and ethnicity and will be summarized by treatment group using descriptive statistics for each of the defined samples and for the effectiveness analyses. Baseline variables are defined as pre-randomization variables such as baseline function or symptom score, comorbidities or any other variables thought to be associated with primary or secondary outcomes, moderate intervention (subgroups) or predict drop-out. Candidate variables will include but are not limited to age, sex, race, ethnicity, rural/medically underserved residency, multiple pain conditions, mental health mood disorders, and negative social determinants of health (SDOH).

Descriptive statistics for all follow-up data will be provided by intervention arm. These descriptive statistics will include the mean, median, SD, maximum and minimum for continuous variables, and frequencies, percentage, and tabulations for categorical variables. Summary statistics will be performed on patient demographics, including age, sex, race, ethnicity, and other clinical characteristics, including medical history, and prior and concomitant interventions.

Subgroups defined by cut points are: 1) sex (male), 2) age (≥ 65 years), 3) race/ethnicity (White/Non-Hispanic, Black or African American/Non-Hispanic, Hispanic, Other), 4) rural/medically underserved residency, 5) multiple pain conditions (>1 pain condition based on ICD dx), 6) mood disorders (anxiety or depression based on ICD dx), and 7) negative/poor SDOH. Additional analysis of groupings of these factors will be dictated by group size and balance between groups.

14.0. Primary Effectiveness Analyses

Primary Outcome Statistical Hypothesis: Both active interventions (painTRAINER and virtual coach-led CBT-CP) are expected to result in a higher proportion of patients achieving MCID (30% reduction in overall BPI-SF score) in pain severity relative to those receiving usual care at 3-month follow-up (primary time point).

Secondary Time Point Statistical Hypotheses: Both active interventions (painTRAINER and virtual coach-led CBT-CP) are expected to result in a higher proportion of patients achieving MCID (30% reduction in overall BPI-SF score) in pain severity relative to those receiving usual care at the 6 and 12-month follow-ups (secondary time points).

Primary Outcome and Secondary Time Point Analyses: We will use modified Poisson regression^{20,21} fit using generalized estimating equations (GEE) to model the binary primary outcome, MCID in pain severity (30% reduction from baseline), 3 months (primary time point) and 6 and 12 months (secondary time points). We are employing modified Poisson (i.e., Poisson family with log link, but use robust standard errors to correct for mis-specified outcome variance) instead of logistic regression since the binary outcome is not rare and the estimate of interest is the relative risk. We will use a working independence correlation matrix and will calculate standard errors using the robust sandwich estimator to account for within-person and within-health coach correlation^{21,22} and account for the mis-specified mean-variance structure when using Poisson regression for a binary outcome.^{20,23} We will include interactions between each intervention and indicators of time (3, 6, 12 months) to estimate time-specific intervention effects; the primary comparisons will be between the interventions and usual care at 3 months (i.e., primary effectiveness will test the size of the intervention coefficient at the 3-months timepoint). We will adjust for baseline levels of pain severity, other stratification variables (sex, clinical site, and rural/medically underserved residency), and a priori variables predictive of outcome (multisite pain and co-occurring mental health condition). Specifically, we will fit the following mean model where Usual Care and 3 months are the reference groups:

$$\log(E(Y_{ij})) = \beta_0 + \beta_1 Int1_i + \beta_2 Int2_i + \beta_3 T6_{ij} + \beta_4 T12_{ij} + \beta_5 Int1_i T6_{ij} + \beta_6 Int2_i T6_{ij} + \beta_7 Int1_i T12_{ij} + \beta_8 Int2_i T12_{ij} + \beta_z Z_i$$

where Y_{ij} is the binary outcome for participant i ($i=1,\dots,n$) and time point j ($j=1,2,3$), $Int1_i$ is 1 if the participant i is randomized to the first intervention group and 0 otherwise, $Int2_i$ is 1 if participant i is randomized to the second intervention group and 0 otherwise, $T6_{ij}$ is 1 if outcome is measured for participant i at 6-months ($j=2$) and 0 otherwise, $T12_{ij}$ is 1 if outcome is measured for participant i at 12-months ($j=3$) and 0 otherwise and Z_i is a vector of baseline adjustment covariates.

In addition, we will conduct a sensitivity analysis to address a change in study procedures that occurred after the study launched. Specifically, to improve engagement in the painTRAINER intervention the study team added motivational interviewing-based language to the onboarding script for those randomized to the online program. This change was implemented on 8/9/2021 after ~140 patients were enrolled in the study. The sensitivity analysis will repeat the primary analysis amongst only those who were randomized after 8/9/2021, this allows to evaluate whether after implementation of the "enhancement" to the painTRAINER engagement activities, there may be a stronger intervention effect.

All analyses will be conducted following an intent-to-treat (ITT) approach, including all individuals randomized regardless of their engagement with or exposure to the intervention.

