11/23/20	Clarified that sample of patients who do not complete the active interventions and will participate in qualitative interviews are still enrolled in the study. This is already specified in section 9.1, which has not been edited, but text was added to other places in protocol where these interviews are described. 3.5 Qualitative Evaluation Objectives 6.1 Recruitment of Patients 11.3 Qualitative Interviews	Add text to clarify in response to VUMC IRB questions
11/24/20	Added text to indicate virtual intervention sessions completed by secure video encounter that are recorded will generate a video recording 2.4.1 Potential Risks 17 Source Documents	Finalization of procedures related to recording virtual sessions
11/24/20	Added [name] as staff person involved in intervention supervision and fidelity monitoring 10.4 Study Intervention Fidelity Monitoring Procedures	Finalization of staff/study team roles
03/22/21	Updated info on number of health coach interviews from "up to 10" to reflect that all coaches (currently projected at 12 so described as "approx.12") will be offered to complete an interview 1.1 Synopsis 6.2 Recruitment of Stakeholders for Qualitative Evaluation 11.3 Qualitative Interviews	Finalization of hiring/staffing of health coaches

Date	Description of Change (Include specific sections affected)	Rationale for Change
03/31/21	Modified EHR-based inclusion criteria related to the minimum number of pain-related encounters (criterion #4 in section 5.1) for the 3 KP sites; changed to ≥ 2 encounters that are at least 30 days apart. Essentia remains at least 1 encounter. 5.1 Participant Inclusion Criteria	High rate of refusal prior to screening due to no chronic pain and ineligibility among those screened at KP sites. By increasing threshold for required pain visits, more likely to efficiently identify people likely to have chronic pain.
03/31/21	Added an EHR-based exclusion criterion related to surgery in the past 60 days for all sites 5.2 Participant Exclusion Criteria	High rate of refusal and reporting recent surgery and therefore no current chronic pain. By adding criterion, more likely to efficiently identify people likely to have chronic pain.
03/31/21	Added exclusion criterion related to planned/scheduled surgery in next year. 5.2 Participant Exclusion Criteria 7 Eligibility Screening	Multiple virtual health coach intervention participants have indicated upcoming surgery; common exclusion criterion for pain studies

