10.1.2 Virtual Coach-led CBT-CP

Overview. The coach-led program includes 8 sessions of CBT-CP provided one-on-one via telephone or video encounters. Each session takes 60 minutes and provides interactive training in one or more evidence-based pain-coping skills. Sessions are scheduled at the participant's convenience with approximately one session per week and participants have the option of meeting with the coach by telephone only, using video conferencing or a combination of the two. The live virtual-enabled coaching provided can enhance patient motivation and engagement. This approach is likely to be especially useful for depressed or anxious patients (common chronic pain comorbidities) for whom de-activation and/or avoidance may create barriers to implementing effective pain-coping skills. Coaches providing these virtual visits are required to have at least master's-level behavioral health training and conduct coaching sessions from the study sites at KPWHRI in Seattle and KP CHR in Portland. This telehealth model of centralized behavioral health services is being widely adopted across health care systems nationally, and thus represents a critically important approach for this active arm of the study.

Onboarding. Following randomization, participants assigned to Virtual Coach-led CBT-CP are mailed materials that include a brief biographical description of their health coach and a participant workbook with handouts for the 8 sessions and materials for logging skills practice. The assigned coach calls the participant approximately one week after the materials are mailed. The primary goal of this outreach by the coach is to introduce themselves and to "onboard" the participant to the program. The onboarding call includes verifying receipt of the packet of materials and orienting the participant to the Virtual Coach-led program structure and format. Participants are informed that coaching calls are confidential, asked their preference for telephone or video coaching calls and for permission to record all coaching calls. The coach will use the onboarding call as an opportunity to respond to questions from the participant and to schedule the first coaching call. Coaches follow specified guidelines to complete the onboarding call which include suggested language/scripting.

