15.1 Sample Size Determination

For the primary study outcome, clinically meaningful improvement (MCID; 30% reduction in overall BPI-SF score) in pain severity at 3 months, sample size requirements were calculated for a two-sided comparison of independent proportions with 90% power using Fisher's Least Significant difference method to account for three-way comparisons (specifically conduct Omnibus Wald Test for any difference between three groups and then conduct pairwise comparisons given an overall difference is statistically significant at the 0.05 alpha level). Sample size calculations assumed a usual care outcome rate of 15% who achieve the MCID of 30% reduction in pain severity from baseline to 3 months. The 15% usual care rate was chosen because this rate was observed among participants in the usual care arm of the study PI's recently completed PPACT trial⁷¹ and it is similar to rates observed by others in the usual care arm of similar trials.⁸⁵ The necessary sample size of 1,863 (621 per arm) was calculated to detect a difference of 7.5% between a given intervention group relative to usual care in the proportion of individuals who attain a clinically meaningful change (30% reduction from baseline) in pain severity. A retention rate of 80% is estimated. Thus, to achieve this final sample size, at least 2,331 individuals will be randomized, 777 per intervention arm. A 7.5% detectable difference corresponds to 22.5% (relative change of 150%) of individuals in an intervention arm attaining a clinically meaningful change in pain severity.

Power for secondary analyses related to aim 1b (subgroup analyses) was also estimated. Sample size requirements for these secondary analyses were calculated using the same assumptions described above (i.e., a two-sided comparison of independent proportions using Fisher's Least Significant difference approach to account for three-way comparisons, with sample size calculations assuming an improvement rate of 15% in the usual care arm). The subgroup sample size was projected to range between 20% and 40% of the original 1,863 sample size since this should cover the range of the subgroup sample sizes of interest.

Power for Subgroup Analyses Ranging the Size of the Subgroup

Assumptions		80% Power to Detect:		
Subgroup Sample Size	Usual Care (UC)	Intervention (Int)	Detectable Difference	Relative Change
N (% of 1,863)	% UC	% Int	% Int - %UC	% Int / %UC
372 (20%)	15.0%	31.0%	16.0%	206.7%
558 (30%)	15.0%	27.7%	12.7%	184.7%

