15.3 General Approach to Statistical Analyses

All confidence intervals and p-values will be two-sided and statistical significance at the 0.05 level.

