5.0. Sample Size Determination for the Primary and Secondary Effectiveness Analyses

For our primary study outcome, clinically meaningful improvement (MCID; 30% reduction in overall BPI-SF score) in pain severity at 3 months, we calculated sample size requirements for a two-sided comparison of independent proportions with 90% power using Fisher's Least Significant difference method to account for three-way comparisons (specifically conduct Omnibus Wald Test for any difference between three groups and then conduct pairwise comparisons given an overall difference is statistically significant at the 0.05 alpha level). Sample size calculations assumed a usual care outcome rate of 15% who achieve the MCID of 30% reduction in pain severity from baseline to 3 months. The 15% usual care rate was chosen because we observed this rate among participants in the usual care arm of our recently completed PPACT trial¹⁷ and it is similar to rates observed by others in the usual care arm of similar trials.¹⁸ We calculated the necessary sample size of 1,863 (621 per arm) to detect a difference of 7.5% between a given intervention group relative to usual care in the proportion of individuals who attain a clinically meaningful change (30% reduction from baseline) in pain severity. We estimate a retention rate of 80%. Thus, to achieve this final sample size, we will randomize 2,331 individuals, 777 per intervention arm. A 7.5% detectable difference corresponds to 22.5% (relative change of 150%) of individuals in an intervention arm attaining a clinically meaningful change in pain severity.

We also estimated power for secondary analyses related to aim 1b (subgroup analyses). We calculated sample size requirements for these secondary analyses using the same assumptions described above (i.e., a two-sided comparison of independent proportions using Fisher's Least Significant difference approach to account for three-way comparisons, with sample size calculations assuming an improvement rate of 15% in the usual care arm). We ranged our subgroup sample size between 20% and 40% of the original 1,863 sample size since this should cover the range of the subgroup sample sizes of interest.

Power for Subgroup Analyses Ranging the Size of the Subgroup

Assumptions		80% Power to Detect:		
Subgroup Sample Size	Usual Care (UC)	Intervention (Int)	Detectable Difference	Relative Change
N (% of 1,863)	% UC	% Int	% Int - %UC	% Int / %UC
372 (20%)	15.0%	31.0%	16.0%	206.7%

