10.0. Multiplicity

We have one primary outcome: minimal clinically important difference (MCID) in pain severity at 3 months. To control for multiple comparisons due to 3 intervention groups we will apply Fisher's Least Significant Difference approach in which first an omnibus Wald test for any statistically significant difference between the three groups is evaluated at the 0.05 alpha level and the pair-wise differences are then evaluated, each using two-sided alpha=0.05, only if the omnibus test is statistically significant. In addition, secondary analyses will use a similar approach as that described for the primary outcome to control for the three group comparisons.

For safety outcomes, multiplicity will not be considered since this study was not powered to observe safety.

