15.0. Secondary Effectiveness Analyses (Secondary Outcomes)

Secondary Outcomes (Aim1a) Primary Statistical Hypotheses: Those in both active intervention conditions will show greater improvements in overall pain severity, pain intensity (MCID and overall), pain-related interference (MCID and overall) and related quality of life outcomes (social role functioning, physical functioning, and patient global impression of change) relative to those receiving usual care at the 3-month follow-up.

Secondary Outcomes (Aim1a) Secondary Statistical Hypotheses: Those in both active intervention conditions will show greater improvements in overall pain severity, pain intensity (MCID and overall), pain-related interference (MCID and overall) and related quality of life outcomes (social role functioning, physical functioning, and patient global impression of change) relative to those receiving usual care at the 6- and 12-months follow-ups (secondary time points).

Secondary Outcomes (Aim 1a) Analyses: Aim 1a will examine the impact of the active interventions on secondary outcomes. Analyses of these outcomes will follow the same proposed approach as Aim 1. We will use linear regression for continuous outcomes and Poisson regression for binary and count outcomes. We will use GEE^{21,22} to estimate regression models for longitudinal data using an independence working correlation matrix. We will calculate all standard errors using the robust sandwich estimator^{21,22} to account for within-person and within-health coach correlation or any misspecified variance structures. We will include an interaction between intervention arms and time indicators, and the primary time point for all secondary analyses will be 3 months following randomization and will include as covariates baseline levels of pain severity and all stratification variables.

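### Within-coach correlation is handled by a plain sandwich and Wald tests, mildly too liberal with about 12 coaches, and the stated 90% power makes no allowance for coach clustering

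*SAP*

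**What the plan says.** SAP 14.0 fits a modified Poisson model by GEE with working independence to the 3-, 6- and 12-month outcomes. It says the team "will calculate standard errors using the robust sandwich estimator to account for within-person and within-health coach correlation". SAP 15.0 uses the same estimator for the secondary outcomes, "to account for within-person and within-health coach correlation or any misspecified variance structures". The SAP's summary of changes shows that coach clustering was added to sections 14.0 and 15.0 in September 2020 on a DSMB recommendation.

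For testing, SAP 10.0 sets an omnibus Wald test at 0.05; the "pair-wise differences are then evaluated, each using two-sided alpha=0.05, only if the omnibus test is statistically significant". Protocol 15.3 adds: "All confidence intervals and p-values will be two-sided and statistical significance at the 0.05 level". Neither document names a finite-cluster correction, a degrees-of-freedom rule or a t/F reference.

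On the number of clusters, the 03/22/21 entry in the Protocol's summary of changes revised the interview count to "reflect that all coaches (currently projected at 12 so described as" about 12). Protocol 6.2 and 11.3 carry the same approximate figure. The number of coaches who actually delivered sessions is not given.

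On power, SAP 5.0 "calculated sample size requirements for a two-sided comparison of independent proportions with 90% power", and Protocol 15.1 says the same. Both give 621 analysed per arm for 15% versus 22.5%, inflated only for 80% retention. No ICC, design effect or coach count appears, and the change log lists no revision of section 5.0 when coach clustering was added.

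**The concern.** The sandwich estimator and its normal or chi-square reference are large-sample tools in the number of clusters. The usual-care and painTRAINER arms each have hundreds of independent participants, but the coach arm has about 12 clusters. Two things then go wrong for any contrast involving that arm: the estimated variance is too small on average, and the estimate of that variance is itself noisy, which the 1.96 cut-off ignores. Coach-led versus usual care is one of the two primary comparisons, and its variance also enters the omnibus gate that painTRAINER must pass.

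The power statement has a related gap. Section 14.0 accepts that outcomes may be correlated within coach, while section 5.0 still offers 90% for every intervention-versus-usual-care comparison as if they were not. A null coach-led result could be read as coming from a 90%-powered comparison when it did not.

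**Working it through.** **Inputs.** Usual care 15%, intervention 22.5%, 621 analysed per arm, retention 80% (SAP 5.0); two-sided 0.05 with omnibus gate (SAP 10.0); 12 coaches (Protocol). The documents give no ICC, so 0, 0.005, 0.01, 0.02 and 0.05 are assumed. Caseloads are equal unless stated: 621/12 = 51.75 analysed per coach.

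**Reproducing the plan's figure.** The ordinary two-proportion formula gives 568 per arm. The method the SAP names (omnibus and pairwise test both significant), simulated on independent data with both active arms at 22.5%, gives 90.0% power at 606 per arm and 90.8% at 621. Then 621/0.8 = 776.25, rounded up to 777, and 3 × 777 = 2,331. The stated size is explained without any margin for coach clustering.

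**Size of the standard-error problem (log relative risk, 3 months).**
- Usual-care variance: v0 = 0.85/(0.15 × 621) = 0.00913.
- Coach-arm variance: v2 = (1 − p)/(621p) × DE, with DE = 1 + 50.75 × ICC, i.e. 1.00, 1.25, 1.51, 2.02 and 3.54.
- With 12 equal clusters the plain sandwich recovers on average 11/12 of v2. The standard error is therefore multiplied by √(1 − s/12), where s = v2/(v0 + v2).
- Satterthwaite df = (v0 + v2)²/(v2²/11 + v0²/620).

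With no coaching effect (p = 0.15):
- ICC 0: s = 0.50, standard error 2.1% too small, df 43, t cut-off 2.02.
- ICC 0.05: s = 0.78, standard error 3.3% too small, df 18, t cut-off 2.10.

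Referring 1.96 × √(1 − s/12) to those t distributions gives two-sided errors of 6.2% and 7.4%, i.e. coverage of 93.8% and 92.6%.

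**Simulation of the planned procedure.** Coach arm beta-binomial over 12 coaches, other arms binomial; omnibus 2-df Wald above 5.99, then |z| above 1.96. Ranges run over ICC 0 to 0.05 and span independent runs of 60,000 to 200,000 replicates per setting.

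| Quantity | Planned test |
|---|---|
| Omnibus error, no arm works | 5.9-7.1% |
| Any false claim against usual care, no arm works | 4.7-6.1% |
| Gated coach-vs-usual-care error, no arm works | 3.4-4.3% |
| Gated coach-vs-usual-care error, only painTRAINER works | 5.9-7.4% |
| 95% interval coverage, coach-led vs usual care, no coaching effect | 92.6-94.2% |
| 95% interval coverage, 15% vs 22.5% | 93.2-94.3% |

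Strongly unequal caseloads (7 to 96 patients per coach) raise the fourth row to 6.3-8.7%. With 8 coaches it is 6.4-8.9%; with 20, about 5.5-6.2%.

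With the Kauermann-Carroll correction (each squared coach residual divided by 1 − m/n, m being that coach's caseload and n the arm size), Satterthwaite t and a matching F, error returns to about 4.8-5.3% and coverage to about 95%. Very unequal caseloads at ICC 0.05 stay at about 5.6-5.9%.

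**Check on the full SAP 14.0 model** (three time points, covariates with assumed effects, 6,000 replicates per setting, Monte Carlo standard error about 0.3 points), ICC 0, 0.01, 0.02, 0.05: omnibus error 6.6, 6.9, 6.1, 7.1%; gated coach error with only painTRAINER working 6.2, 6.0, 6.7, 7.5%, or 4.7-5.5% corrected.

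**Power, coach-led versus usual care, planned gated test, 12 coaches.**

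| ICC | 621 per arm, both arms work | 621, only coaching works | 683 per arm |
|---|---|---|---|
| 0 | 91% | 92% | 93% |
| 0.005 | 88% | 88% | 91% |
| 0.01 | 85% | 84% | 88% |
| 0.02 | 80% | 77% | 83% |
| 0.05 | 67% | 60% | 69% |

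The 683 is 777 × (1 − 0.121), from the 12.1% missing all follow-ups in the SAP's 07/17/24 entry. It is an upper bound for 3-month data. With 20 coaches and 621 per arm the figures are 91, 89, 88, 84 and 75%. painTRAINER versus usual care stays at 89-91%.

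A closed-form check without the gate, Φ(log 1.5/√(v0 + v2) − 1.96), gives 90.0% at ICC 0.0035, 89.2% at 0.005 and 86.6% at 0.01.

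**The case against.** The plan already does the important thing: it recognises coach clustering and puts it in the variance. Calling the estimator uncorrected reads silence as a choice, since nothing rules out a correction. That is fair, but an analyst following the text would run the default, and a prespecified plan should not leave this open.

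The error excess is also small where claims are made. If neither arm works, the gate keeps the coach-versus-usual-care error below 5%, and any false claim against usual care is at most about 6.1%. The clear excess needs painTRAINER to work and coaching not to, whereas SAP 1.3 expects coaching to be possibly the more effective. All of this stands and limits the weight of the point. It does not remove the interval shortfall, which is present in every scenario, including ICC 0.

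The coach count is uncertain. The figure of about 12 may include staff who support painTRAINER, so the true number could be lower, which is worse; at 20 the excess shrinks but remains.

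The power loss rests on an ICC the documents do not give. At ICC 0 the claim holds, and the largest losses need 0.05. Enrolment cannot now change, so that part only corrects a statement.

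Finally, the imputation and weighting of SAP 11.0 and the continuous secondary outcomes were not simulated, so the exact figures may not carry over to them.

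**Conclusion.** Both parts hold. With 12 coaches the planned procedure is mildly liberal for the coach arm: about 1 to 2.5 points of excess error in the omnibus test and, when only painTRAINER works, in the coach comparison, plus about 1 to 2.5 points of lost coverage. This does not depend on a positive ICC, but it does depend on the coach count and grows with fewer coaches or uneven caseloads. painTRAINER's own contrast is not inflated.

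The 90% power describes painTRAINER versus usual care. For coach-led versus usual care it holds only if clustering is close to zero; at 621 analysed per arm it is about 85% at ICC 0.01 and 80% at 0.02. The ICC values are assumptions and missing-data handling was not modelled. This is worth correcting before unblinding, but it does not undermine the trial.

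**What to change.** **Analysis (SAP 14.0 and 15.0, before unblinding).**
- Name a bias-corrected sandwich such as Kauermann-Carroll, Satterthwaite t for contrasts and intervals involving the coach arm, and a matching F for the omnibus test.
- State that the cluster is the assigned coach in the coach arm and the participant in the other two. Protocol 10.1.2 supports assignment as the definition: "The assigned coach calls the participant approximately one week after the materials are mailed".
- Report how many coaches delivered sessions and their caseloads.

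**Power statement (SAP 5.0 and Protocol 15.1).** Say that the 90% assumes no coach clustering, and give coach-arm power over a range of ICCs using the actual number of coaches.

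**Cost.** SAP wording, a software option, and the protocol amendment that SAP 2.0 requires when the primary analysis changes. The coach-led interval becomes 3-11% wider. Coach-arm gated power with 12 coaches falls from 90.9 to 89.3% at ICC 0, from 85.4 to 82.7% at 0.01, and from 66.6 to 60.8% at 0.05. painTRAINER loses about 0.5-2 points because the F gate is stricter. No extra patients are needed, and restating the power changes no estimate or test.
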